Key safety assessments	

Adverse event monitoring

Physical examination

Vital signs

Laboratory evaluations, including anti-AMG 334 antibody testing

Electrocardiogram (ECG)

Other assessments	

Patient reported outcomes (PROs)

Modified Migraine Disability Assessment Questionnaire (mMIDAS)

Beck Depression Inventory-II (BDI-II)

Clinical Outcome Assessments (COAs): eDiary

Data analysis	
The primary efficacy endpoint variable will be analyzed using a generalized linear mixed model based on observed monthly data during the treatment period.
 
The secondary efficacy endpoints will be analyzed using a linear mixed effects model similar to the primary endpoint. The dichotomous endpoints will be analyzed by Cochran-Mantel-Haenszel (CMH) test with subjects who are missing monthly migraine day data during the last 4 weeks of treatment period imputed as non-responders. Nominal 95% confidence intervals and p-values will be reported. Tests of secondary endpoints will be tested at nominal 2-sided significant level 0.05.

Key words	AMG 334, erenumab, migraine, chronic, headache, Chinese

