### **12.4.1 Definition of primary endpoint(s)**

The primary efficacy endpoint is the change from baseline in monthly migraine days during the last 4 weeks of the 12-week treatment period. The monthly migraine days will be calculated using data collected from the eDiary.

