### **12.4.2 Statistical model, hypothesis, and method of analysis**

The null hypothesis is that there is no difference in the change from baseline in monthly migraine days in the last 4 weeks of the 12-week treatment period between erenumab group and placebo group versus the alternative hypothesis that there is a difference between the two groups. The null hypothesis will be rejected if the observed p-value for the between-group comparison is less than the significant level adjusted according to the alpha spending function with the O'Brien-Flemming approach. The nominal p-value threshold will be calculated upon the exact information collected in the interim analysis, considering the alpha-level spent at interim analysis and considering the actual correlation among the test statistics, in order to achieve a cumulative type I error smaller than the desired significance level (i.e. smaller than the 5% for a two-sided test). The primary efficacy endpoint variable will be analyzed using a generalized

linear mixed model with treatment, scheduled visit, treatment by visit interaction, and the stratification variables and baseline values as covariates. If applicable, unstructured covariance structure is assumed. Least squares means (LSMs) for treatment groups and its associated 95% confidence intervals, difference of LSMs compared to placebo group and the associated 95% confidence interval of the difference, as well as the nominal two-sided p-values, will be tabulated by visit and treatment.

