2.5.2 Statistical hypothesis, model, and method of analysis

The primary endpoint of the study will be tested for erenumab 70 mg compared to placebo.

Null hypothesis: There is no difference between erenumab 70 mg group and placebo group, in terms of change from baseline in monthly migraine days in the last 4 weeks of the 12-week treatment period.

Alternative hypothesis: There is a difference between erenumab 70 mg group and placebo group, in terms of change from baseline in monthly migraine days in the last 4 weeks of the 12-week treatment period.

The null hypothesis will be rejected if the observed p-value for the between-group comparison is less than the significant level adjusted according to the alpha spending function with the

O'Brien-Flemming approach. The nominal p-value threshold will be calculated upon the exact information collected in the interim analysis, considering the alpha-level spent at interim analysis and considering the actual correlation among the test statistics, in order to achieve a cumulative type I error smaller than the desired significance level (i.e. smaller than the 5% for a two-sided test).

The primary efficacy endpoint variable will be analyzed using a linear mixed effects repeated measures model based on observed monthly data during treatment period, with treatment, scheduled visit, treatment by visit interaction, and the stratification factors and baseline values as covariates. If applicable, unstructured covariance structure is assumed. Least squares means (LSMs) for treatment groups and its associated 95% confidence intervals, difference of LSMs compared to placebo group and the associated 95% confidence interval of the difference, as well as the nominal two-sided p-values, will be tabulated by visit and treatment.

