2.5.4 Sensitivity analyses

Multiple imputation (MI) techniques applying missing at random (MAR) and missing not at random (MNAR) approaches will be used to assess the impact of missing values on the interpretation of the results during study. In addition, the baseline observations carried forward (BOCF) method will also be used. After imputation, the primary efficacy variable at week 12 will be analyzed using an analysis of covariance (ANCOVA) model including treatment group and stratification factor as fixed effects in the model with baseline value as covariate.

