- Furthermore, an option is used at post-baseline visits (modelobs= (trt01p='Placebo')) to include an adjustment for the fact that any missing data from active treatment subjects will be similar to placebo subjects under the assumption that missing values in the active treatment subjects implies they are no longer on treatment. That is, an imputation model for the missing data in the active treatment group is constructed not from the observed data in the active treatment group but rather from the observed data in the placebo group. This model is also the imputation model that is used to impute missing data in the placebo group.

MAR and MNAR modeling step:

- For the change from baseline in MMD analysis, it uses a linear mixed effects repeated measures model on imputing data under the assumption of MAR or MNAR. There is no gaps in imputed data, therefore, all the data is available to analyze and can use a fixed effects model looking only at the avisitn=2012/week12 data.
- If necessary, for the 50% Responders analysis, it is based on imputed MMD data under the assumption of MAR or MNAR. Then, use the same method as for primary analysis - the stratified CMH test to get estimates for numbers of responders in each treatment group and odds ratio at week 12 for each dataset.

MAR and MNAR combining step:

- The output dataset with the treatment LS means (LSMEANS) and the treatment differences (DIFF) are then sorted, manipulated and read into proc mianalyze to combine the individual sets of imputed results into one set of overall results, see all steps SAS codes in TFLs document.

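### Primary repeated-measures model applies one baseline slope to Weeks 4, 8 and 12; adding baseline-by-visit and stratum-by-visit terms is a free, small gain in precision and makes the model consistent with the Week 12 ANCOVA

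*Protocol*

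**What the plan says.** The endpoint is a single-visit quantity: "The primary efficacy endpoint is the change from baseline in monthly migraine days during the last 4 weeks of the 12-week treatment period". It is estimated from a model of all three monthly values. The protocol summary says "The primary efficacy endpoint variable will be analyzed using a generalized linear mixed model based on observed monthly data during the treatment period" and names no covariates; the terms are in Protocol 12.4.2, "linear mixed model with treatment, scheduled visit, treatment by visit interaction, and the stratification variables and baseline values as covariates", and are repeated in SAP 2.5.2, "with treatment, scheduled visit, treatment by visit interaction, and the stratification factors and baseline values as covariates". On covariance, SAP 2.5.2 says: "If applicable, unstructured covariance structure is assumed".

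Neither list crosses baseline or the stratification factors with visit, and no fuller model statement settles the matter. SAP 2.6.2 and 5.1.5.3 refer the reader to Sections 5.4 and 5.4.1 for the models. Section 5.4 covers exclusions from analysis sets and has no 5.4.1, and Section 5.3 describes only the Van Elteren test.

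The sensitivity analyses use a different covariate model. After imputation, SAP 2.5.4 fits an "analysis of covariance (ANCOVA) model including treatment group and stratification factor as fixed effects in the model with baseline value as covariate" to the Week 12 value. SAP 5.1.5.3.2 likewise notes that, once the data are complete, one "can use a fixed effects model looking only at the avisitn=2012/week12 data".

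**The concern.** With baseline as a main effect, the regression of change on baseline is held equal at the three visits, and so are the stratum effects. Under an unstructured covariance the common slope is a precision-weighted compromise in which the less variable visits count most. If the relation to baseline changes over the 12 weeks, the Week 12 comparison is corrected for chance baseline imbalance with a slope that is not its own.

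Two things are at stake. Some of the precision available from baseline adjustment may be lost. The primary estimate and the Week 12 ANCOVA may also disagree for a reason unrelated to missing data, although the purpose of SAP 2.5.4 is to show the effect of missing data.

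**Working it through.** **The plan's own figure first.** Inputs from Protocol 12.8.1: difference 2.0 days, SD 6.8, two-sided 0.05, 90% power, 1:1, 10% dropout.

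- n per arm = 2(1.960 + 1.282)² × 6.8² / 2.0² = 243, so 486 in total, and 486/0.90 = 540. The stated 550 is within 2%.
- With 550 × 0.90 = 495 evaluable subjects, power is 90.5% at 0.05. Allowing for the interim look (p 0.014, final p 0.0459 against the stated 0.046), it is 90.2%.

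This is an unadjusted two-mean calculation and does not depend on the baseline slope.

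**How the slope enters.** With complete data, either model gives

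Week 12 effect = (difference in mean change) − slope × (difference in mean baseline).

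The written model uses the common slope b; the ANCOVA uses its own slope β12. Hence:

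- gap between the two estimates = (β12 − b) × baseline imbalance, with SD |β12 − b| × SDx × 2/√495;
- Week 12 variance ratio = 1 + (β12 − b)² × SDx² / residual variance at Week 12.

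The imbalance has mean zero under randomisation, so neither model is biased.

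**Assumed inputs (none are in the documents).** Baseline SD (SDx) 4.5 or 5.5; MMD SD 6, 6.5 and 7 at Weeks 4, 8 and 12; residual correlation 0.6 to 0.75, either decaying with the gap between visits or equal between all visits. The slope of change on baseline at visit t is r_t × SD_t/SDx − 1, where r_t is the correlation with baseline. The common slope b minimises log|S + (β − b)(β − b)′SDx²|, where S is the residual covariance matrix of the three visits.

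**One case in full.** SDx 5.5, r = 0.65/0.55/0.45, decaying residual correlation 0.75. The slopes are −0.291, −0.350 and −0.427, and b = −0.314. The residual variance at Week 12 is 49 × (1 − 0.45²) = 39.08. The excess is 0.113² × 5.5² = 0.39, and 0.39/39.08 = 1.0%. The SD of the gap is 0.113 × 5.5 × 2/22.25 = 0.056 days.

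| Correlation with baseline, Weeks 4/8/12 | Excess Week 12 variance, decaying | Same, equal correlation | SD of gap, decaying (days) |
|---|---|---|---|
| 0.60/0.55/0.50 | 0.01–0.02% | 0.02–0.03% | 0.01 |
| 0.65/0.55/0.45 | 0.8–1.0% | 1.0–1.5% | 0.05–0.06 |
| 0.70/0.50/0.40 | 2.9–4.1% | 3.6–5.7% | 0.10–0.12 |

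Power at the extreme corner (two-sided 0.05, 495 subjects): residual variance 49 × (1 − 0.40²) = 41.16, so the ANCOVA SE is √(41.16 × 4/495) = 0.577 and power is Φ(2/0.577 − 1.96) = 93.4%. With 5.7% more variance the SE is 0.593 and power is 92.1%, a loss of 1.3 points. At that corner the SD of the gap is √0.057 × 0.577 = 0.14 days.

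**Simulation on separate assumptions.** 4,000 complete-data trials per scenario, 247 per arm, Week 12 SD 6.8, baseline SD 4 or 6. Ten scenarios were run; six are shown.

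| Slopes, Weeks 4/8/12 | SE common vs own slope, SDx 4 | SE common vs own slope, SDx 6 | Median absolute gap (days) |
|---|---|---|---|
| −0.4/−0.4/−0.4 | 0.588 vs 0.588 | 0.568 vs 0.568 | 0.006 |
| −0.3/−0.4/−0.5 | 0.587 vs 0.584 | 0.558 vs 0.554 | 0.03–0.05 |
| −0.1/−0.3/−0.6 | 0.584 vs 0.572 | 0.538 vs 0.519 | 0.08–0.10 |

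Over all ten scenarios, bias was at most 0.014 days, and the 95% interval of the common-slope model missed the true value in 4.6 to 5.2% of trials. Its SE always stayed below the unadjusted SE (0.605 to 0.620). In the last row power fell from 93.7% to 92.5% (SDx 4) and from 97.0% to 95.7% (SDx 6), and the 95th percentile of the gap was 0.24 to 0.30 days.

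**The case against.** The strongest reply is that the written model is valid and prespecified. Baseline as a main effect, treatment-by-visit and unstructured covariance give an unbiased Week 12 contrast under randomisation, and the simulation supports that. The planned power comes from an unadjusted SD of 6.8, and the common-slope model still beat the unadjusted comparison in every simulated scenario. All of this stands; what remains is a matter of efficiency and consistency.

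A reader might infer two stronger things that the documents do not support.

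- **That the Week 12 estimate is under-adjusted.** This needs a Week 12 slope steeper than the common slope, and the documents give no slopes, baseline SD or between-visit correlations. A correlation with baseline that weakens over time is not enough, because a rising SD works against it. With correlations 0.60/0.58/0.56, SDs 6/6.5/7 and SDx 5.5, the slopes are −0.345, −0.315 and −0.287. With equal residual correlation of 0.6 the visits get weights of about 0.54, 0.31 and 0.15, so the common slope is about −0.33, and Week 12 is over-adjusted.
- **That differences among the results could no longer be traced to missing data.** SAP 2.5.4 applies the same Week 12 ANCOVA after multiple imputation under missing at random (MAR), after multiple imputation under missing not at random (MNAR), and after baseline observation carried forward (BOCF). Comparing MNAR and BOCF with MAR imputation therefore isolates the missing-data assumption, with or without a change to the primary model.

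Nor would the added terms make the primary result equal to the MAR-imputation result when data are missing. The imputation dataset in SAP 5.1.5.3.2 brings in sex, race, age and BMI groups, number of failed prophylactics and disease duration, and imputes continuous variables by predictive mean matching.

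**Conclusion.** The point holds as a free improvement. As written, one baseline slope and one set of stratum effects apply at all three visits. The cost is precision only, and its size rests entirely on the assumed inputs above: nothing if the slope is constant, up to about 1.5% of Week 12 variance for moderate change, and about 3 to 6% if the relation to baseline falls steeply. The typical gap from the Week 12 ANCOVA is small beside an SE of roughly 0.52 to 0.59 days. The validity of the test, the 550-subject calculation and the stated power of about 90% are unaffected. The calculations treat the primary analysis as the normal linear repeated-measures model named in SAP 2.5.2, with unstructured covariance and complete data.

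**What to change.** In Protocol 12.4.2 and SAP 2.5.2, add baseline-by-visit and stratification-factor-by-visit interactions to the primary model. In SAP 2.6.2, do the same for mMIDAS and monthly acute headache medication days. With complete data and unstructured covariance, the Week 12 estimate then equals the Week 12 ANCOVA, provided that the ANCOVA carries both stratification factors; SAP 2.5.4 has the word in the singular and should name both. If the sponsor prefers a common slope, say so and give the reason.

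While editing, put the full model statement in the SAP and correct the references to Sections 5.4 and 5.4.1.

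The cost is one line of text in each place and in the program. Two extra parameters for baseline and two for each of the two binary strata make six, against about 495 × 3 = 1,485 monthly records. If the slopes turn out equal, the loss is negligible: the simulated SEs agreed to three decimals. The change should be made before any unblinded data are seen.

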## 1 Introduction

### 1.1 Background

Migraine is a common worldwide occurring neurological disorder throughout all regions and ethnicities with a high global prevalence, significant socio-economic burden and substantial impairment and disability of affected patients. It has a global prevalence of 11% in adults ([Stovner et al 2007](#)). The first headache epidemiological survey across the China mainland showed that the estimated 1-year prevalence of migraine is 9.3% ([Yu et al 2012](#)). It is mainly characterized by recurrent headache lasting 4-72 hours but is usually accompanied by other neurological disturbances, nausea, vomiting and other nonspecific symptoms. The patient burden and disability as well as the societal impact increase with higher attack frequency, which is why the spectrum of migraine disorders is typically described according to frequency of migraine days per month. “Episodic migraine” (EM) is characterized by migraine with fewer than 15 headache days per months, while “Chronic migraine” (CM) is defined as 15 or more headache days per months, at least 8 out of which have to be typical migraine days. According to World Health Organization (WHO), CM is one of the most disabling disorders as it imposes a substantial effect on day-to-day functioning. Compared with individuals with EM, those with CM are much more likely to be unemployed, be divorced, and have psychological comorbidities, suggestive of the burden of the disease on the individual, their families, and society ([Buse et al 2013](#)). Based on the high frequency of migraine and effect on quality of life, patients with CM are good candidates for preventive therapy. In general, EM and CM patients share many common features in terms of the clinical presentation, which include the headache pain features and associated symptoms. The distinction between EM and CM is somewhat arbitrary and numerous lines of evidence support that they are a continuum of the same disorder.

Migraineurs are currently being treated for migraine prophylaxis by a variety of drug classes, many of them being used off-label and often based on insufficient or limited evidence. In particular in CM, despite its enormous burden, there are few well-controlled studies for migraine prophylaxis with quality evidence available, only for onabotulinum toxin A and topiramate. Other therapies such as  $\beta$  blockers or amitriptyline are frequently used, despite a lack of evidence in patients with CM. Oral preventive therapies available at present, including topiramate,  $\beta$  blockers, and amitriptyline are often not fully efficacious or are poorly tolerated, which can lead to low adherence rates. Botulinum toxin (Botox®) is approved in many countries for CM use, but not for EM. In China, there is only 1 drug, flunarizine, approved for migraine prophylaxis.

Nontraditional therapies such as herbal medicines, supplements, acupuncture and other therapies also have some role in migraine prophylaxis. While the evidence supporting their use is minimal and often controversial ([Gooriah et al 2015](#)), they are very common in the Asian region, and becoming more widespread and increasingly introduced into mainstream Western healthcare.

Based on emerging evidence, Calcitonin Gene-related Peptide (CGRP) is a neuropeptide that prominently contributes to migraine pathophysiology. The potential mechanisms of action of CGRP receptor antagonists involve components of the trigeminal-vascular system and include normalization of CGRP-induced vasodilation, reduction of CGRP-induced neurogenic inflammation, and inhibition of pain transmission at the trigeminal ganglion and trigeminal

nucleus ([Wang et al 1995](#), [Zimmermann et al 1996](#), [Durham 2006](#)). CGRP is an attractive target for the development of a migraine-specific prophylactic therapy with the aim of minimizing migraine days and improving patient quality of life in this common and often disabling disorder.

Erenumab (AMG 334) is a fully human monoclonal antibody targeting the CGRP receptor under development for migraine prophylaxis in adults. To date studies have been, or are currently being, conducted in North America, Europe, Japan and some other Asian countries/regions. Erenumab is already approved in United States of America (USA), European Union (EU) and other countries for the preventive treatments of migraine in adults. As of 31 January 2019, approximately 4613 patients with migraine have taken this medicine in clinical studies to date including over 200 patients who had >4 years of maximum treatment duration. The confirmed good safety and tolerability of erenumab does not suggest increased risks for patients with longer exposure.

Results from the erenumab Phase 2 study (Study 20120178) in patients with episodic migraine demonstrated that the 70 mg dose resulted in statistically significant and clinically meaningful reductions in monthly migraine days at Week 12 compared with placebo. The 70 mg dose produced statistically significant improvements in multiple secondary and exploratory outcome measures, including the 50% responder rate, monthly headache days, and monthly migraine-specific medication treatment days. Exposure-response pharmacokinetic (PK) analyses over a large range of PK exposures indicated that 70 mg was the lowest dose resulting in efficacious concentrations and potentially higher efficacy could be achieved with 140 mg. Based on this results, a higher dose of 140 mg was incorporated into the following pivotal studies. Results from the erenumab Phase 2 study (Study 20120295) in patients with chronic migraine also showed a positive outcome. Patients randomized to the 70 mg and 140 mg dose groups experienced a mean 6.6-day reduction from baseline in monthly migraine days during Weeks 9-12 in both groups. The results were statistically significant compared with 4.2 days observed in the placebo group. The 50% responder rate was 39.9% and 41.2% with 70 mg and 140 mg erenumab respectively compared to 23.5% with placebo. Both doses were also effective across various other endpoints including frequency-related outcomes and functional improvement measured by established Patient Reported Outcome (PRO) scales ([Tepper et al 2017](#)).

The results from two completed Phase 3 studies (Studies 20120296, 70 and 140 mg, and 20120297, 70 mg) in patients with episodic migraine, also showed positive outcomes for erenumab. In Study 20120297, patients randomized to the 70 mg dose group experienced a 2.9-day reduction from baseline in monthly migraine days compared with 1.8 days observed in the placebo group with the difference being statistically significant ([Dodick et al 2018](#)). In study 20120296, patients randomized to the 70 and 140 mg dose groups experienced mean 3.2 and 3.7-day reductions from baseline, respectively compared with a 1.8 days observed in the placebo group over weeks 13-24 ([Goadsby et al 2017](#)). Results for both of these studies were statistically significant. Fifty percent responder rates were significantly increased with erenumab compared to placebo in both of the Phase 3 episodic migraine studies. Treatment effects observed with 140 mg in Study 20120296 showed consistently higher values across different parameters and subgroups compared to placebo than the 70 mg group, suggesting additional efficacy in global patients with episodic migraine.

Apart from the global clinical program focused on Caucasian population, a Phase 1 study in Japanese subjects (Study 20120130) and a Phase 2 study (Study 20120309) in Japanese subjects with EM were conducted to support the registration in Japan. The PK of erenumab at 70 mg was similar and there is no ethnic difference between healthy Japanese and Caucasian subjects. Study 20120309 is a Phase 2, multicenter, randomized, double-blind, placebo-controlled, parallel-group study. A total of 475 subjects were randomized 2:1:2:2 to receive placebo, erenumab 28 mg, 70 mg, or 140 mg during the 24-week double-blind treatment phase. While the results were significant for all 3 doses evaluated, the efficacy on the primary and secondary endpoints for the 28 mg dose were almost 50% lesser in magnitude than the 70 mg dose. Comparable efficacy was seen between 70 mg and 140 mg doses. Besides, the safety profile was similar to placebo and also comparable between Japanese and Caucasian subjects. A multi-regional, three arms (placebo, 70 mg and 140 mg groups), double-blinded, Phase 3 study (Study CAMG334A2302) in the EM population, primarily in Asia is currently ongoing. The purpose of this study is to obtain data from regions not adequately represented in the global pivotal trials, and to support registration in countries or regions requiring local data for regulatory approval (India, Korea, and Taiwan).

The safety and tolerability profile of erenumab was similar to placebo in both treatment groups for all studies. No adverse event (AE) occurred with an incidence of > 6%; the most commonly reported adverse events included injection site pain, infection of the upper respiratory tract and nausea. Based on a pooled analysis across four placebo-controlled trials, the identified adverse drug reactions include injection site reactions, constipation, muscle spasm and pruritus.

In view of limited information on ethnic subgroups, especially Chinese, this trial will provide additional information about erenumab safety and efficacy in CM in a mainly Chinese population and provide local data for regulatory submission.

